In this step, signal acquired from every selected channel would be averaged. There are fifteen signals from the instruction that are averaged into one signal representing the instruction.

Short Time Fourier Transform (STFT)

STFT will be used to determine a dominant frequency from the signal of an ensemble average result when the event occurs.

Event Related Desynchronization/Event Related Synchronization

ERD/ERS during event is calculated with the above data.

2) Meditation

Subjects will be introduced to Isha Kriya (IK) meditation. IK is a meditation that can be learned quickly and requires approximately 12 minutes, twice a day of practice. This regimen was chosen because of its simplicity making it an excellent way to introduce meditation to beginners. IK does not incorporate a spiritual or religious focus. [name], the principal investigator of the study, was trained to be an instructor by the Isha Institute of Inner Sciences, a nonprofit foundation located at McMinnville, Tennessee.

At the time of enrollment, [name], or a trained research team member, will provide a brief introduction to IK meditation and review a handout of the meditation instructions. The subjects can utilize the online-guided meditation or follow the instructions on their own.

Preparation: Sit in a cross-legged posture or sit in a chair, spine comfortably erect, hands upon thighs, palms facing up, face slightly upturned, eyes closed, keeping a mild focus between the eyebrows.

Meditation: Slow inhaling and exhaling while mentally focusing on the words "I am not the body" and "I am not even the mind" for 7 minutes; uttering a long "Ahh" sound seven times; sitting for 5 minutes with eyes closed.

Subjects will be asked to practice the meditation twice daily for 12 minutes each session, for approximately 6 weeks. They will be given a meditation diary to complete daily.

	Baseline	After 6 weeks
Group 1 - Novice meditators	Meditation with EEG monitoring	Meditation with EEG monitoring
Group 2 - Experienced meditators	Meditation with EEG monitoring	Meditation with EEG monitoring

Study Monitoring / Adverse Events:

The study interventions are non-invasive and minimal risk. Therefore, we will limit the scope of AE monitoring and reporting to the following:

- All Serious Adverse Events believed to be related to the study procedures
- Unexpected, non-serious Adverse Events believed to be related to the study procedures

B. Statistical Considerations

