- Sample Size Justification:** In this pilot study, atleast10 patients who complete both EEGs are required for analysis. In order to achieve this target accrual of 10 patients and also to account for potential dropouts, a total of 15 volunteers will be recruited.
- Data Analysis:** Continuous data will be reported as means \pm standard deviation or median (quartile 1, quartile 3) depending on distribution. Normality will be assessed with the Shapiro-Wilk test. Categorical data will be reported as frequencies and proportions and assessed with a chi-square or Fisher's Exact test as appropriate. SAS 9.4 (SAS Institute Inc., Cary, NC) will be used for all analyses, with two-sided p-values < 0.05 considered statistically significant.

The primary aim of the study is to study the effect of guided meditation on EEG. This will be a descriptive study noting the EEG changes (alpha vs beta), differences in the waveform signals between novices and experienced meditators, and at the beginning and the end of the 6-week period. Secondary analysis is being conducted with collaborators outside of BIDMC. [name], [name] & his subordinate [name] from The University of Houston; will be assisting in the analysis of the EEG data collected. They will be provided with limited de-identified dataset in accordance to the terms of specific Data Use Agreements. No PHI will be shared between the institutions and all data will be completely de-identified before secure transfer to the co-investigators.

Primary endpoint:

- 1) Examine the qualitative EEG measures associated with Isha Kriya meditation
 - Event related potential fields in EEG: amplitude in fT and latency in ms
 - Oscillations: power spectral density and time-frequency oscillations in fT²/Hz

Secondary endpoints:

- 1) Investigate the difference in EEG changes between novice and experienced meditators
- 2) Investigate the difference in EEG changes between the start and end of 6 weeks of daily meditation

C. Subject Selection

This is a descriptive study of healthy volunteers, including novices and expert meditators.

Inclusion criteria:

- 1) 18 years or older
- 2) Novice or expert meditator

Novice meditator: No meditation practice in the previous year and < 20 entire lifetime hours

Expert meditator: Meditation \geq 30 min per day for at least 5 days per week over the past 1 year

Exclusion criteria:

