This meditation regimen was chosen because it excels in simplicity and is a great way to introduce meditation to beginners. It does not incorporate a spiritual or religious focus. Subjects who are unable to consent for themselves will be excluded from this study.

B7. STUDY LOCATION

Privacy

Study interactions and procedures will take place in private clinical settings with curtains/doors closed so as to provide privacy and comfort. Every effort will be made to protect the privacy of the participant.

Physical Setting

Subjects will be enrolled at BIDMC. Prescreening will occur via phone. Consent and EEGs will be performed in either the Clinical Research Center (CRC) or Pre-admission Testing (PAT) clinic. Electronic data will be maintained on password-protected computers behind the institutional firewall. Paper records will be maintained in locked file cabinets and secure research offices.

B8. DATA SECURITY

All electronic data will be stored in REDCap and/or on password-protected servers behind the BIDMC firewall. Any data collected on paper will be stored in locked file cabinets or in secure offices. Each subject will be assigned a study-specific ID number. A crosswalk between the participants and their study IDs will be maintained on password-protected computers by members of the research team. Limited information will be retained on patients who are prescreened and do not qualify, or who are approached and declined, for the purposes of generating a CONSORT diagram.

Any transfer of data to outside collaborators will be done by sending Limited Data Sets with date-shifting, using Secure File Transfer. Data will be completely de-identified and transferred in a secure manner. The de-identified data will be loaded in memory drive and/or DVD and send via trackable FedEx or using a Secure File Transfer online. Recipients will work with the data on their secure institutional computers, behind a firewall. All data sharing will be done in accordance to the terms of BIDMC-issued Data Use Agreements.

B9 Multi-Site Studies

N/A – not a multi-site study

Is the BIDMC the coordinating site? Yes No

Is the BIDMC PI the lead investigator of the multi-site study? Yes No

B10 Dissemination of Research Results

Participants will be thanked for their time throughout the study. There is no plan to share the results at the conclusion of this trial.

References:

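### The plan does not provide for masking to group or visit while EEG channels are selected and waveforms read, though both secondary comparisons are group or visit contrasts

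*Combined protocol and SAP*

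**What the plan says.** The Ensemble Average step in B3.A states that "signal acquired from every selected channel would be averaged". It does not say which channels these are, by what rule they are selected, by whom, or when.

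The Data Analysis text in B3.B describes a descriptive study that will note "differences in the waveform signals between novices and experienced meditators, and at the beginning and the end of the 6-week period". The same two contrasts are the secondary endpoints, and one two-sided 5% threshold is set for all analyses. The primary endpoint is to "Examine the qualitative EEG measures associated with Isha Kriya meditation".

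On who does the work, B3.B says that collaborators at another institution "will be assisting in the analysis of the EEG data collected" and adds: "They will be provided with limited de-identified dataset in accordance to the terms of specific Data Use Agreements". The variables in that dataset are not listed.

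B8 (Data Security) says: "Each subject will be assigned a study-specific ID number". It continues: "A crosswalk between the participants and their study IDs will be maintained on password-protected computers by members of the research team". For outside transfers: "Any transfer of data to outside collaborators will be done by sending Limited Data Sets with date-shifting". No section mentions masking or blinding of EEG processing, reading or analysis.

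**The concern.** Three things come together. First, at least one influential step is open: which channels enter the average. The background in B2 reports alpha increases at both frontal and posterior sites, so the choice of location can shape the answer. Second, the expected direction is known in advance: B2 reports more alpha and theta activity in meditators than in non-meditators, and the study asks whether this technique gives changes in line with the literature. Third, nothing in the plan keeps group and visit out of sight while the open choices are made.

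When labels are visible, reasonable judgements can drift toward the expected result without any intent. Both secondary contrasts could move this way, and with about 10 completers there is little data to dilute the effect. What is at stake is whether a novice-expert or start-end difference can be read as a feature of the recordings and not of how they were handled.

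**Working it through.** **Step 1. Is there any masking?** The processing steps in B3.A, the analysis text in B3.B and the data-handling text in B8 are all present and can be set side by side. None provides for concealing group or visit from anyone who handles the EEGs.

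**Step 2. Which steps are open to judgement?**
- Channel selection (B3.A): open, with no rule.
- Noting waveform differences (B3.B): open, with no method for reading the waveforms.
- Dominant frequency: computed by short-time Fourier transform. ERD/ERS: calculated. Neither is a reading, but both take the average of the selected channels as input.

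**Step 3. Do the existing codes mask?** There is one ID per subject, so both recordings of a subject share it and the ID does not separate visits. Nothing says that the ID or dataset hides group. The method of date-shifting is not given, so visit order may survive. Date-shifting is described only for outside transfers, and the site team holds the crosswalk.

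**Step 4. Sample size.** The plan's own figure is 15 recruited for 10 completers. That implies dropout of 1 - 10/15 = 33.3%. The plan states no rate, so the figure can be neither confirmed nor faulted, and the point does not depend on it.

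**Step 5. Illustration of scale.** The number of choices, their correlation, the shift, the 5 versus 5 split and the t-tests are all assumptions. The plan states no group split and names no test for continuous outcomes.

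*(a) Best of k choices under no true effect.* With independent choices the false-positive rate is 1 - 0.95^k. For k = 5 this is 1 - 0.774 = 22.6%. Correlated choices were simulated with 40,000 null trials per setting (paired t, n = 10; two-sample t, 5 versus 5). The two designs agreed closely.

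| Choices k | Independent | Correlation 0.8 |
|---|---|---|
| 1 (no selection) | 5% | 5% |
| 2 | 9.8% | about 8% |
| 5 | 22.6% | about 14% |
| 10 | 40.1% | about 19% |

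*(b) A systematic shift of b SD toward the expected direction.* The rejection rate comes from the noncentral t distribution. The noncentrality is b × √10 (9 df) for the paired comparison and b / √(2/5) (8 df) for 5 versus 5. At b = 0.5 these are 1.58 and 0.79.

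| Shift b | Paired, n = 10 | 5 versus 5 |
|---|---|---|
| 0 | 5% | 5% |
| 0.2 | 8.8% | 5.9% |
| 0.3 | 13.6% | 7.0% |
| 0.5 | 29.3% | 10.8% |

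A choice made without sight of the labels cannot be steered by them, so under no true effect the rate stays at about 5%. These figures show what could happen under the stated assumptions. They are not estimates for this trial.

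**The case against.** The strongest reply is that the plan is silent, and silence is not unmasked analysis. That stands. A reader might infer that analysts will know group and visit. The documents do not say so: they list no variables in the transferred dataset and do not say who selects channels. Only the absence of a masking provision is established.

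A reader might also take the whole pipeline to be subjective. It is not. The frequency and ERD/ERS steps are computed, and the items listed under the qualitative primary endpoint are numeric (amplitude, latency, spectral power). The text does not describe epoch selection. What remains is channel selection and the noting of waveform differences.

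A third tempting inference is that masking comes free because files are already coded and date-shifted. Step 3 above shows that it does not. Nor should weight be placed on the principal investigator being a trained instructor of the technique, since the documents do not say that this person reads or processes EEGs. The lack of a control group is a separate matter that masking would not cure.

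Finally, it can be said that a pre-specified channel and band rule would deal with selection directly. That is correct for illustration (a). Masking protects whatever judgement such a rule leaves.

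**Conclusion.** The concern holds in a limited form. The plan makes no provision for masking to group or visit during EEG channel selection and waveform reading, and its privacy measures do not supply one. The exposure is confined to the two secondary comparisons: the primary endpoint describes EEG during meditation and has no group or visit contrast to mask. The study is a small descriptive pilot, so no confirmatory claim depends on this. A significance threshold is nevertheless applied to those comparisons.

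The documents give no basis for estimating the size of any bias, and the rates above rest wholly on assumed inputs. The change is worth making because it alters what is done, protects both contrasts and costs little.

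**What to change.** Before any EEG is processed, and before any file leaves the site:

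1. Give each recording, not each subject, a random code that reveals neither group nor visit.
2. Have everyone who processes the EEGs, at the site or outside, work under that code. They fix the channel selection, any data exclusions, the extracted EEG values and any waveform descriptions recording by recording.
3. Lock these, with a date. A research-team member who does no EEG processing holds the key linking code to subject, group and visit, and releases it only after the lock. The pairing of visits and the group comparison follow from the key.
4. State the channel and band rule in the plan as well.

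The cost is a re-coded file list, a key-holder and a lock step, carried by a team that already keeps the ID crosswalk. Visits, procedures and sample size do not change.
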